9.6 Subject Disposition

Evaluable Subjects

- **Enrolled Subjects:** subjects who sign the study's informed consent form
- **Randomized Subjects:** subject who remain free from arrhythmia recurrence after signing the study ICF and are randomized into one of the study arms (OAT withdrawal or OAT).
- **Completed Subjects:** enrolled subjects who have not been discontinued, withdrawn or lost-to-follow-up from the study prior to the final (12 month) study visit.
- **Lost to Follow-up Subjects:** subjects who are enrolled and randomized, but contact is lost after most recent follow-up visit (despite 3 documented attempts to contact the subject, two (2) by documented telephone calls, and one (1) written attempt sent by registered mail).
- **Discontinued:** Subjects that have arrhythmia recurrence at any time during the Evaluation Period will be discontinued. Discontinued subjects are exited from the study prior to completion of all follow-up visits; however, they will remain in the analysis cohort until the time at which they are discontinued from the study.
- **Withdrawn Subjects:** Subjects may be withdrawn for reasons stated below in Section 9.7. Withdrawn subjects are exited from the study prior to completion of all follow-up visits; however, they will remain in the analysis cohort until the time at which they are withdrawn.

Non-Evaluable Subjects

- **Excluded:** Subjects found to not meet one of the study inclusion/exclusion criteria after the being enrolled.

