10.0 Study Endpoints

10.1 Primary Endpoint

The primary endpoint is a composite endpoint represented by the occurrence of any major thromboembolic event (stroke [i.e., ischemic, hemorrhagic or cryptogenic] that is an acute onset of a focal neurologic deficit of presumed vascular origin lasting for ≥ 24 hours or resulting in death) or major hemorrhagic complication (major bleeding) during the 12-month Evaluation Period.

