12.4 Outcome

Regarding the outcome of each AE, the investigator will assess and evaluate the relationship according to the following classifications:

Table 6: Adverse Event Outcome Classifications

Classification	Definition
Resolved without sequelae	Subject fully recovered with no observable residual effects
Resolved with sequelae	Subject recovered with observable residual effects
Improved	Subject's condition improved, but residual effects remain
Unchanged	AE is ongoing
Worsened	Subject's overall condition worsened
Death	Subject died as a result of the AE

12.5 Adverse Event Documentation and Reporting Requirements:

AE information will be collected throughout the study and will be recorded on eCRFs. The investigator is responsible for ensuring that all AEs observed by the investigator or reported by the subject that occur from the time that the subject has signed the informed consent through the end of the study are properly assessed, recorded, and reported as defined and described in the Adverse Events Section (12.0) of this protocol. All AEs must be assessed by the study investigator and properly documented by completing the subject's medical records (source documents) and appropriate eCRF. Additional documentation may be requested by the Sponsor, including but not limited to, a written subject narrative detailing the clinical course of the AE, a copy of any correspondence with the local EC/EB, and extracts from medical records (patient identifiers removed). All AEs will be monitored until they are adequately resolved or explained.

Table 8: AE Reporting Requirements

Type of Adverse Event	Reporting Requirements
Non-Serious and Anticipated Adverse Events	Report to Sponsor within 7 days of awareness
Serious Adverse Events	Report to Sponsor within 24 hours of awareness
Unanticipated AEs	Report to Sponsor within 24 hours of awareness
Subject Death	Report to Sponsor within 24 hours of awareness

The Sponsor will confirm that (serious) AEs are reported as required to the:

- **To Institutional Review Board (or equivalent):** The site is responsible for ensuring that all (serious) AEs are fully recorded and reported to the IRB (or equivalent) according to the local requirements.

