13.4 Analysis Population

The study contains two treatment arms with subjects either discontinuing OAT or continuing OAT. The primary analysis will be based on the intent-to-treat principle where subjects will be analyzed by the group to which they are randomized, regardless of actual treatment received. Lost-to-follow-up, discontinued, and withdrawn / early termination subjects will also be included in this analysis.

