13.7 Endpoint Analyses

13.7.1 Primary Endpoint Analysis

The primary endpoint is the occurrence of any thromboembolic event or major hemorrhagic complications during the 12-month Evaluation Period.

The Kaplan-Meier method will be used to model the time to the first occurrence of any thromboembolic event or major hemorrhagic complications during the 12-month Evaluation Period following randomization. The survival probabilities of the occurrence of any thromboembolic event or major hemorrhagic complications at the 12 month follow-up along with the corresponding 95% confidence intervals will also be presented. The equality of the survival curves between two randomization groups will be tested by the Log-rank test.

This analysis will include all subjects in the analysis population and account for censored observations. Subjects lost to follow-up, withdrew or discontinued prior to reaching their primary endpoint will be censored at their last visit.

Descriptive statistics such as 25th percentile, median and 75th percentile of time to the first occurrence as well as the 95% confidence intervals around the median time will be presented overall and by randomization groups.

The number and proportion of subjects experiencing occurrence of any thromboembolic event or major hemorrhagic complications will be summarized overall and by two randomization groups at 12 month follow up. The Fisher exact test will be used to compare the proportions between the two randomization groups.

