13.7.2 Analysis of Secondary Endpoints

Descriptive statistics including frequency and percentage for categorical secondary endpoints will be presented. The categorical secondary endpoints include minor hemorrhagic events (minor bleeds), hospitalization with any thromboembolic or major hemorrhagic event, all cause mortality, AF recurrence and repeat ablation procedures for AF.

The 95% confidence intervals for binary outcome will be computed using exact binomial method. Descriptive statistics and 95% confidence intervals will be presented overall and by randomization groups. The proportion of the occurrence will be compared between randomization groups using the Fisher exact test.

Descriptive statistics for continuous endpoints will include number of subjects, mean, standard deviation, median, 25th and 75th percentiles, minimum and maximum. These continuous secondary endpoints include the index scores of the SF-36. Change from baseline for the index score of the SF-36 will be compared between two randomization groups using the Wilcoxon rank sum test.

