13.7.2.3 All Cause Mortality (%)

Descriptive statistics of subjects who die during the 12-month Evaluation Period will be summarized by randomization groups. Causes of death will be listed and summarized by randomization groups.

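### Loss to follow-up is declared after three attempts directed only at the subject, so a death or disabling stroke in either arm can itself cause the censoring and go uncounted

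*Combined protocol and SAP*

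**What the plan says.** - **Definition of loss (9.6).** A randomized subject is lost when contact has ended "despite 3 documented attempts to contact the subject, two (2) by documented telephone calls, and one (1) written attempt sent by registered mail". All three attempts are addressed to the subject.
- **Time-to-event analysis (13.7.1).** "Subjects lost to follow-up, withdrew or discontinued prior to reaching their primary endpoint will be censored at their last visit".
- **Population (13.4).** The primary analysis is by intention to treat: "Lost-to-follow-up, discontinued, and withdrawn / early termination subjects will also be included in this analysis".
- **Comparison of proportions (13.7.1).** "The Fisher exact test will be used to compare the proportions between the two randomization groups". No rule is given for a subject whose 12-month outcome is unknown, and the denominator is not stated.
- **Endpoint (10.1).** The composite joins major bleeding with stroke of any type "that is an acute onset of a focal neurologic deficit of presumed vascular origin lasting for ≥ 24 hours or resulting in death". Fatal and disabling strokes are therefore primary events.
- **Mortality (13.7.2 and 13.7.2.3).** "Descriptive statistics including frequency and percentage for categorical secondary endpoints will be presented", and "Descriptive statistics of subjects who die during the 12-month Evaluation Period will be summarized by randomization groups". Again no denominator is stated, and there is no rule for unknown vital status.
- **Reporting of deaths and serious events (12.5, Table 8).** "Report to Sponsor within 24 hours of awareness". The clock starts only once the site knows of the event.

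**The concern.** Kaplan-Meier estimates and the log-rank test are valid if censoring carries no information about the outcome. Here it may. A subject who has died, or who is in hospital or a nursing facility after a severe stroke, is the subject least able to answer a telephone or sign for a letter. Three unanswered attempts are enough to assign the status, and the analysis then treats that person like someone who moved house.

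Two results are exposed: the primary composite, which can lose fatal or disabling strokes and fatal bleeds, and all-cause mortality, which can lose any death. Mortality is also the endpoint least open to judgement in an unblinded trial. Section 13.3 disclaims power, so the trial's main product is its event counts by arm, and those counts are expected to be small.

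**Working it through.** **1. Does another section repair the rule?**

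| Provision | Does it find an unknown event in an unreachable subject? |
|---|---|
| 12.5, Table 8: prompt reporting of deaths and serious events | No. It starts from awareness. |
| 9.7, 12.0, 12.5: follow adverse events to resolution | No. It covers events already known. |
| 12.5, 15.6: safety committee review | No. It receives what sites have reported. |
| 15.4: investigator follows subjects to the end of the protocol | A general duty, with no method for a subject who cannot be reached. |
| 13.7.1: sensitivity analysis for lost subjects | None planned. |

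No section requires a second contact, a physician, hospital records, death records or a closing check of vital status.

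**2. One subject followed through the rules (illustration).** Table 3 sets visits at 3, 6 and 12 months. Suppose a subject in either arm is seen at month 6 and has a fatal stroke at month 8, treated elsewhere. Two calls and a letter go unanswered.
- 9.6: lost to follow-up.
- Kaplan-Meier and log-rank: censored at month 6, so the month 8 event never enters the curve.
- Fisher comparison and mortality percentage: the event is absent from the numerator. Whether the subject is in the denominator is not stated.

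The gap between the last visit and the next scheduled contact can be 12 − 6 = 6 months.

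**3. Size.** The plan states no loss rate, event rate, margin or effect size, so there is no figure of its own to reproduce.
- Weight of one missed event, with 50 per arm (13.3): 1/50 = 2 percentage points.
- Exact (Clopper-Pearson) 95% intervals: 0/50 gives 0 to 7.1%; 1/50 gives 0.05 to 10.7%; 2/50 gives 0.5 to 13.7%.
- Scale of expected counts, using 5.1: major bleeding on anticoagulation 1.5 to 4.2 per 100 patient-years, and untreated stroke roughly 2 to 10. The lowest and highest of these give 50 × 0.015 = 0.75 and 50 × 0.10 = 5 events per arm for a single component. These are general atrial fibrillation populations; 5.2 reports very few thrombotic events after successful ablation, so true counts may be lower.
- Subjects lost, assuming 2%, 5% or 10%: 50 × 0.02 = 1, 50 × 0.05 = 2.5, 50 × 0.10 = 5 per arm.
- Outer bounds, with all hidden events in the Test arm. Observed 1 v 1 (Fisher p = 1.00) becomes 3 v 1 with two hidden (p = 0.62) and 6 v 1 with five hidden (p = 0.11). Observed 1 v 0 (p = 1.00) becomes 6 v 0 with five hidden (p = 0.027). These are extremes, not forecasts.

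**4. Direction.** Let p_T and p_C be the true event proportions, and h_T and h_C the fractions missed.
- Observed minus true difference = h_C·p_C − h_T·p_T.
- If the fraction missed is the same, h, in both arms, the observed difference is (1 − h)(p_T − p_C). It shrinks towards zero whichever arm is worse.
- If the fractions differ, the sign depends on four quantities, none of which the documents give for this population.

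**The case against.** **The definition is not a ceiling.** Section 9.6 describes a disposition category and does not forbid further tracing. A relative may answer the telephone or the letter, and 15.4 obliges the investigator to follow subjects to the end. The consent form and eCRFs are separate documents and may hold alternate-contact provisions. This stands as a limit on what can be claimed: sites may do better than the rule. But nothing in this plan makes them, and a site that follows 9.6 exactly can record a fatal stroke as a loss.

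**It is an unpowered pilot.** Section 13.3 says so, and the intervals above overlap heavily: one missed event moves an arm from 0 to 7.1% to 0.05 to 10.7%. No formal decision would turn on that. This also stands, and it limits the severity. It does not make the gap harmless, because 13.1 still states a non-inferiority objective and each event carries 2 percentage points.

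**A reader might infer that the rule favours withdrawal**, since 5.3 names thromboembolism as the main risk of stopping treatment and most bleeds leave a subject able to answer. The documents do not support that as a finding. The same section names hemorrhagic stroke, alongside major bleeding, as the Control-arm risk, and Table 2 counts symptomatic intracranial bleeding as major. Those events can also kill or silence a subject.

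**Conclusion.** The concern holds as a gap in outcome ascertainment. Under 9.6 and 13.7.1 together, a death or disabling stroke in either arm can produce its own censoring and be missed in the primary endpoint and in all-cause mortality. The net direction is uncertain. With similar under-ascertainment in both arms the difference shrinks towards zero, which is the unhelpful direction for a non-inferiority question. The size cannot be estimated because no loss rate is given; the firm figure is 2 percentage points of an arm per missed event.

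Two further readings are tempting and go beyond the documents.
- **That a large share of any true excess would vanish.** From 5.1, 2.7/0.62 = 4.35% per year stroke off treatment and 4.35 − 2.7 = 1.65% on it. Adding 1.2% per year bleeding on treatment, over an assumed 1% background, gives a composite difference of (4.35 + 1.0) − (1.65 + 2.2) = 1.5 points. Assuming 10% to 30% of strokes and 5% of bleeds are hidden leaves 1.29 to 0.75 points. The relative loss looks big, but it is 0.21 to 0.75 points, or about 0.1 to 0.4 of one subject in 50. The hidden fractions have no source in the plan, and the stroke rates assume that ablation protects nobody.
- **That lost subjects are counted as alive and event-free at 12 months.** The Kaplan-Meier analysis counts them event-free only to the last visit. For the Fisher comparison and the mortality percentage this is an inference, true only if the denominator is all randomized subjects.

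The change should be made. The gap does not invalidate the trial.

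**What to change.** **Section 9.6.** Before a subject may be classed as lost, require the site to:
- try an alternate contact and the treating or primary-care physician, both named at consent;
- check its own hospital records and, where law allows, death records;
- record vital status, stroke status, major-bleed status and the date last known event-free.

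**Section 13.7.1.** Count events found this way at their onset date. Censor the remaining lost subjects at the date last known event-free, in place of the last visit. Report by arm the number whose vital status or event status stays unknown. State the denominators for the Fisher comparison here and for mortality in 13.7.2.

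**Sensitivity analysis, if one is added.** Limit it to subjects truly lost, and apply best-case and worst-case assumptions to both arms. It should not count every Test subject with unknown 12-month status as an event. Sections 9.6, 11.2.1 and 11.3 exit subjects for AF recurrence, and Test subjects for resuming anticoagulation, so their 12-month status is unknown by design. If 10% to 20% of Test subjects recurred (assumed), that would create 50 × 0.10 = 5 to 50 × 0.20 = 10 artificial events. Because resuming treatment triggers exit only in the Test arm, a one-sided analysis would also be unbalanced.

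**Cost.** One consent line, one eCRF field for status, and slightly more site work for each lost subject. Contact details stay at the site and only the status reaches the sponsor, which fits 14.3. No treatment, visit or eligibility rule changes.

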8.3 Number of Centers

Up to 10 sites will be included in the study. Total subject enrollment is expected to be 100. All subjects enrolled will be followed through 12 months after randomization or until AF recurrence.

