8.4 Study Duration, Completion, and Termination

- **Duration:** The study duration is anticipated to be 2 years; 1 year to complete screening/enrollment, and 1 year to complete follow-up for all subjects.
- **Completion:** The study will be considered complete when all subjects either complete their 12-month study visit, withdraw/discontinue the study, become lost to follow-up.
- **Termination:** The study may be terminated prematurely at the discretion of the Sponsor, on statistical grounds, or on the advice/recommendation of the Safety Monitoring Committee. The Sponsor may also terminate a site prior to study completion if it believes the site is no longer capable of participating (eg, cannot fulfill subject enrollment goals, site suspension by IRB or equivalent).

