11.2 Medication Management

11.2.1 OAT Management

Prior to enrollment in the OAT Pilot Study, subjects' OAT should be administered at the discretion of the investigator and in accordance with current AF management guidelines.^{6, 30-32} Subjects should continue their physician-prescribed regimen for OAT until they are enrolled in the OAT Pilot Study. Subjects randomized to the OAT (Control) Group should continue their current OAT regimen; however, changes are allowed per the investigator's discretion (i.e., from one type of OAT to another) during the Evaluation Period. All commercially approved OAT medications may be prescribed to subjects in the OAT (Control) Group. Subjects in the OAT Withdrawal (Test) Group who resume OAT during the Evaluation Period, regardless of the reason, will be discontinued from the study at the time when OAT therapy is resumed.

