11.3 Management of Arrhythmia Recurrence

If there is AF recurrence after the subject is randomized to one of the study arms, the subject should be treated according to institutional Standards of Care (SOC), which is defined as the clinical work flow that physicians follow in their practice (without any mandated protocol requirements) and the processes required by the investigator's institution. Subjects who experience an AF recurrence and/or undergo a repeat ablation or resume OAT (for subjects in the OAT Withdrawal [Test] Group) for AF will be discontinued from the study.

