11.4.3 Unscheduled Visits

If a subject returns for visit outside of the protocol-defined visit windows provided in the Study Visits Section (11.4.1) of this protocol, the visit will be considered "unscheduled". If the unscheduled visit is for any purpose other than a repeat ablation procedure, an unscheduled visit CRF must be completed and the subject must also return for their next scheduled study visit. A list of the requested/recommended assessments that should be performed during the unscheduled visits is included in Table 3.0. If the unscheduled visit is for arrhythmia recurrence, the subject must be discontinued from the study as previously indicated in the Subject Disposition Section (9.6) of this protocol. All appropriate forms (eg, Final Status Form) must be completed for subjects that are discontinued due to arrhythmia recurrence within the Evaluation Period.

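### Follow-up stops at AF recurrence (both arms) or OAT resumption (test arm), so the primary analysis is intent-to-treat by allocation but not by follow-up

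*Combined protocol and SAP*

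**What the plan says.** **Exit at AF recurrence, both arms.** Section 9.6: "Subjects that have arrhythmia recurrence at any time during the Evaluation Period will be discontinued". Section 8.3: "All subjects enrolled will be followed through 12 months after randomization or until AF recurrence". Section 11.3 restates the rule ("Subjects who experience an AF recurrence and/or undergo a repeat ablation or resume OAT"), and 11.4.3 closes the record: "All appropriate forms (eg, Final Status Form) must be completed for subjects that are discontinued due to arrhythmia recurrence within the Evaluation Period".

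**Exit at OAT resumption, test arm only.** Section 11.2.1: test subjects who restart OAT, "regardless of the reason, will be discontinued from the study at the time when OAT therapy is resumed". Control subjects who stop OAT face no matching mandatory rule. Section 9.7 only lets the investigator remove a subject, for example for noncompliance.

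**What happens to the data.** Under 9.6, discontinued subjects leave before their remaining visits, and "they will remain in the analysis cohort until the time at which they are discontinued from the study". Discontinuation also counts towards study completion in 8.4 ("all subjects either complete their 12-month study visit, withdraw/discontinue the study, become lost to follow-up"). Section 13.7.1 censors discontinued subjects at their last visit.

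**What the analysis is said to be.** Section 13.4 specifies intent-to-treat by randomized group whatever treatment was taken, with discontinued subjects included. Sections 10.1 and 13.2 define the primary endpoint over the 12-month Evaluation Period. Section 13.1 states a non-inferiority objective. Section 13.7.1 specifies Kaplan-Meier estimates, a log-rank test, and a Fisher exact test on proportions.

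**The concern.** The question in sections 6.0 and 7.0 is whether OAT can safely be stopped after a successful ablation. Part of that risk arises when AF returns in someone no longer anticoagulated, and observation stops at exactly that point.

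Three consequences follow.

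- **Estimand.** The result describes risk while AF-free in the control arm, and while AF-free and off OAT in the test arm. It does not describe 12-month risk by randomized arm.
- **Censoring.** Kaplan-Meier and log-rank methods need exit to be unrelated to later risk. Section 5.1 says AF raises thromboembolic risk, so exit at recurrence is plausibly informative. Test-arm exits on OAT resumption have no control-arm counterpart.
- **Crude proportions.** Section 13.4 keeps exited subjects in the population, so in the Fisher comparison they count as event-free even though part of their year was not observed.

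Mortality and repeat ablation, described over 12 months in 13.7.2.3 and 13.7.2.5, are cut short in the same way. Repeat ablation is affected most directly, because the recurrence that would prompt it has already ended follow-up.

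**Working it through.** **Step 1: is there any collection after exit?** Three places might provide it.

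- Section 9.7 follows an AE that caused withdrawal until it resolves or stabilizes, and sections 12.0, 12.5 and 15.6 follow reported AEs to resolution. None of these looks for new strokes or bleeds.
- Section 12.5 covers AEs that "occur from the time that the subject has signed the informed consent through the end of the study". No visit or contact is scheduled for a subject who has exited, and 13.7.1 would place any later event after the censoring date.
- Section 13.4 includes discontinued subjects by arm, but 13.7.1 removes their later time.

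So no new endpoint events after exit enter the primary analysis.

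**Step 2: inputs for an illustration.** The plan gives no recurrence rate, event rate, margin or power calculation, so there is no figure to reproduce.

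- 12-month recurrence: 25%, range 15% to 35% (assumed).
- Stroke off OAT: 1%/year before recurrence (assumed). After recurrence 4.35%/year (assumed), derived from 5.1 as 2.7%/0.62.
- OAT cuts stroke by 62% and adds 1.2%/year major bleeding (5.1).
- Bleeding on OAT: 1.5%/year, the lower rate in 5.1. Off OAT: 1.5 - 1.2 = 0.3%/year.
- Constant hazards, the same recurrence rate in both arms, and exit at recurrence.

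**Step 3: person-time lost.** With L = -ln(1 - recurrence), the share lost is 1 - (1 - exp(-L))/L.

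| Recurrence | L | Lost |
|---|---|---|
| 15% | 0.1625 | 7.7% |
| 25% | 0.2877 | 13.1% |
| 35% | 0.4308 | 18.8% |

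**Step 4: shift in risk difference at 25% recurrence.** Composite hazards per year, before and after recurrence:

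- Control: 0.38 x 1% + 1.5% = 1.88%, then 0.38 x 4.35% + 1.5% = 3.15%.
- Test: 1% + 0.3% = 1.30%, then 4.35% + 0.3% = 4.65% if OAT is not resumed, or 3.15% if it is.

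The exit-censored Kaplan-Meier risk is 1 - exp(-h0). The risk with full follow-up is 1 - {exp(-(L+h0)) + L[exp(-h1) - exp(-(L+h0))]/(L + h0 - h1)}.

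Control: Kaplan-Meier 1.86%, full follow-up 2.03%. Test: Kaplan-Meier 1.29%, so the exit-censored difference (test minus control) is -0.57 points throughout.

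| Test-arm exits resuming OAT | Test, full follow-up | Difference, full follow-up | Shift |
|---|---|---|---|
| none | 1.72% | -0.31 | -0.27 |
| half | 1.63% | -0.40 | -0.17 |
| all | 1.53% | -0.50 | -0.08 |

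Shifts are in percentage points, computed before rounding. The largest is about 0.13 events per 50 subjects.

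**Step 5: precision.** With 1/50 events in each arm, the Newcombe 95% interval for the difference is +/-8.65 points. The largest shift is 0.27/8.65, about 3% of that half-width.

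**Step 6: the crude proportion.** A separate illustration assumes 25% recurrence and 4%/year, unchanged after recurrence. The 12-month risk is 1 - exp(-0.04) = 3.9%. The crude proportion is 0.04/(0.04 + 0.2877) x (1 - exp(-0.3277)) = 3.4%. It is too low even though censoring here is uninformative. If the rate tripled after recurrence, full follow-up would give 4.9%, while Kaplan-Meier would stay at 3.9% and the crude proportion at 3.4%.

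**The case against.** The strongest reply is that the exit rule is deliberate and consistently stated, that 13.7.1 discloses the censoring, and that 13.3 says the pilot is not powered for inference. Much of this stands, and it rules out several stronger readings.

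- **That no intent-to-treat analysis can be produced.** A reader might infer this. But 13.4 defines the principle by allocation and includes discontinued subjects, so that version can be run as written. What is missing is follow-up to match it.
- **That the plan measures risk while on the assigned strategy.** It does not. A control subject whose AF recurs while still on OAT is exited, whereas one who stops OAT has no mandatory exit.
- **That the result is biased towards withdrawal.** The shifts above point that way under their inputs. Other plausible inputs point the other way, and the documents do not settle it.
- **That exits will be unequal between arms.** Section 11.4.2 recommends continuous monitoring for the off-OAT group, and resumption exits are one-sided, so this is possible. Table 3, however, lists AF monitoring at 3, 6 and 12 months for both groups, and nothing allows the inequality to be quantified.
- **That the 9.6 and 13.7.1 censoring dates conflict materially.** Moving censoring back to the previous scheduled visit would raise the loss from 13.1% to 17.6%, but only if the last visit means the last scheduled one. Section 13.7.1 does not say so, and 11.4.3 and Table 3 provide for an unscheduled visit at recurrence. This calls for a wording clarification only.

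The pilot label limits inference but does not change what is estimated. The plan still states a non-inferiority objective and runs two tests.

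**Conclusion.** The point holds and should be fixed: the description of the primary analysis is wrong as written. Subjects exit at AF recurrence or, in the test arm, at OAT resumption; no new endpoint events are collected afterwards; and the analysis censors them. That conclusion comes from the text and needs no assumed rate.

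The size does rest on assumptions. Under those above, about 13% of person-time is unobserved (7.7% to 18.8% at 15% to 35% recurrence), and the risk difference shifts by -0.27 to -0.08 points with exit at recurrence. No document supports the 25% recurrence rate for subjects already selected as AF-free, and the model omits unequal exit between arms and OAT resumption for reasons other than recurrence.

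A reader might infer that this bias invalidates the pilot's comparison. The figures do not support that, since the shift is small beside about +/-8.7 points. The reason to act is that events after exit cannot be reconstructed once the study has closed.

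**What to change.** - **Sections 8.3, 8.4, 9.6, 11.2.1, 11.3 and 11.4.3:** separate AF recurrence or OAT resumption from leaving the study. Collect stroke, thromboembolism, major bleeding, death, hospitalization and repeat ablation to month 12 for every randomized subject who has not withdrawn consent.
- **Section 13.7.1, primary analysis:** use all events to month 12 by randomized arm, censoring only at withdrawal of consent, last contact or month 12.
- **Section 13.7.1, supplement:** report the analysis censored at AF recurrence or OAT resumption, labelled *while AF-free (and off OAT in the test arm)*, with exit dates and reasons by arm. It is worth keeping because OAT resumption in the test arm can dilute a true harm under a non-inferiority objective.
- **Wording:** align the censoring date between 9.6 (time of discontinuation) and 13.7.1 (last visit).

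**Cost.** A protocol, consent and eCRF amendment with EC/IRB approval, plus event and vital-status contacts for exited subjects. That is about 15 to 35 of 100 at the assumed recurrence rates, plus other test-arm subjects who resume OAT. Table 3 already schedules the visits, which could be reduced to such contacts, so no procedure is added. No change to the management of recurrence or OAT is proposed.
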